8.4. Pharmacokinetics

Blood samples will be collected for measurement of plasma concentrations of LY3561774 as specified in the SoA.

Participants may need to return to the clinical site for PK-specific visits to provide post-dose PK samples dependent on the time window of PK sampling.

Instructions for the collection and handling of biological samples will be provided by the sponsor. The actual date and time (24-hour clock time) of each sample and the most recent LY3561774 dose prior to PK blood draw must be recorded.

Samples will be used to evaluate the PK of LY3561774. Only samples from participants assigned to treatment with LY3561774 will be analyzed for drug concentration. Samples collected for analyses may also be used to evaluate safety or efficacy aspects related to concerns arising during or after the study.

Intervention concentration information that may unblind the study will not be reported to investigative sites or blinded personnel.

8.4.1. Bioanalytical

Samples will be analyzed at a laboratory approved by the sponsor and stored at a facility designated by the sponsor. Concentrations of LY3561774 will be assayed using a validated bioanalytical method. Analyses of samples collected from placebo-treated participants are not planned.

Sample retention is described in Section [10.1.12](#). Remaining samples used for PK may be pooled and used for exploratory metabolism or bioanalytical method experiments as deemed appropriate.

8.5. Pharmacodynamics

Pharmacodynamic parameters are described in Section [8.1](#).

8.6. Genetics

A whole-blood sample will be collected for pharmacogenetic analysis where local regulations allow. See Clinical Laboratory Tests, and the SoA for sample collection information.

See Section [10.5](#) for genetic research, custody, and Section [10.1.12](#) for sample retention information.

8.7. Biomarkers

Serum and plasma samples will be used for exploratory biomarker research, where local regulations allow. See Clinical Laboratory Tests, and the SoA for sample collection information.

Samples will be used for research on the drug target, disease process, variable response to LY3561774, pathways associated with lipid metabolism, mechanism of action of LY3561774, and/or research method, or for validating diagnostic tools or assay(s) related to lipid metabolism.

Samples may be used for research to develop methods, assays, prognostics and/or companion diagnostics related to the intervention target, disease state, pathways associated with disease, and/or the mechanism of action of the study intervention.

Sample retention is described in Section [10.1.12](#).

8.8. Immunogenicity Assessments

Visits and times

At the visits and times specified in the SoA, venous blood samples will be collected to determine antibody production against LY3561774. The actual date and time (24-hour clock time) of each sample collection will be recorded.

Sample collection, handling, and use

Instructions for the collection and handling of blood samples will be provided by the sponsor.

Immunogenicity may be assessed by a validated assay designed to detect ADAs in the presence of LY3561774 at a laboratory approved by the sponsor. Antibodies may be further characterized for their ability to neutralize the activity of LY3561774.

Samples used for immunogenicity may be used for exploratory analyses as deemed appropriate.

Sample retention

Sample retention is described in Appendix 1, Section [10.1.12](#).

8.9. Health Economics

Health economics parameters are not evaluated in this study.

9. Statistical Considerations

9.1. Statistical Hypotheses

The study hypothesis for the primary objective is if LY3561774 100 mg, 400 mg, or 800 mg is superior in percent change from baseline for ApoB relative to placebo at Day 180 in participants with mixed dyslipidemia.

9.2. Analyses Sets

This table defines the analysis population and datasets for the purposes of analysis.

Population	Description
Screened	All participants who signed informed consent.
Randomized	All participants who are randomly assigned to a treatment arm.
Efficacy Analysis Set (EAS)	Data obtained during the treatment period from all randomly assigned participants who are exposed to at least 1 dose of intervention. Excludes data after permanent discontinuation of intervention. Participants will be included in the treatment group to which they were randomly assigned.
Full Analysis Set (FAS)	Data obtained during the treatment period from all randomly assigned participants who are exposed to at least 1 dose of intervention, regardless of adherence to intervention. Participants will be included in the treatment group to which they were randomly assigned.
Safety Analysis Set (SS)	Data obtained during the treatment period plus safety follow-up from all randomly assigned participants who are exposed to at least 1 dose of intervention, regardless of adherence to intervention. Participants will be included in the treatment group to which they were randomly assigned.

9.3. Statistical Analyses

9.3.1. General Considerations

Statistical analysis of this study will be the responsibility of Lilly or its designee.

Any change to the data analysis methods described in the protocol will require an amendment ONLY if it changes a principal feature of the protocol. Any other change to the data analysis methods described in the protocol, and the justification for making the change, will be described in the CSR. Additional exploratory analyses of the data will be conducted as deemed appropriate.

Unless otherwise noted, all tests of treatment effects will be conducted at a 2-sided alpha level of 0.05, and confidence intervals will be calculated at 95%, 2-sided. All tests of interactions between treatment groups and other factors will be conducted at a 2-sided alpha level of 0.10.

Baseline is defined as the last non-missing measurement recorded on or before the randomization visit, prior to first dose of intervention, unless otherwise specified.

Primary estimand of interest and efficacy assessment

The primary estimand is a precise definition of the treatment effect to be estimated. The primary estimand of interest is comparing efficacy of LY3561774 doses to placebo and is named the “efficacy estimand” (Section 3). The efficacy estimand represents the efficacy prior to discontinuation of intervention.

The primary efficacy assessment guided by the efficacy estimand will be conducted using the EAS (Section 9.2).

Safety assessments

Unless specified otherwise, safety assessments will be guided by an estimand comparing safety of LY3561774 doses with placebo irrespective of adherence to intervention. Thus, safety analyses will be conducted using the SS (Section 9.2).

Exploratory analyses

Additional exploratory analyses of the data will be conducted as deemed appropriate.

Continuous data

Continuous data will be summarized by the sample size, mean, SD, median, minimum, and maximum.

Categorical data

Categorical data will be summarized by sample size, frequency, and percentage.

Analysis models for the comparison among treatment groups

The analysis model for comparisons among treatment groups relative to continuous measurements assessed over time, in addition to the baseline and end of treatment measurements, will be an MMRM. The model terms are

- treatment
- visit
- treatment-by-visit interaction
- baseline measurement, and
- Visit 1 TG stratum ($<250\text{mg/dL}$, $\geq 250\text{ mg/dL}$).

Additional covariates may be added and will be detailed in SAP.

Logistic regression will be used to examine the treatment difference in binary efficacy outcomes. Fisher’s exact test or Pearson’s chi-square test will be used to examine the treatment difference in categorical outcomes. The negative binomial regression model will be used for the treatment comparison of discrete count measures if deemed appropriate.

Other statistical methods may be used, as appropriate, and details will be documented in the SAP.

9.3.2. Primary Endpoint/Estimand Analysis

The primary efficacy assessment, guided by the efficacy estimand, will be conducted using the EAS for the primary endpoint.

For the efficacy estimand, the hypothetical strategy is used to handle the intercurrent events of permanent discontinuation of intervention.

The primary efficacy comparison will be based on the contrast between each treatment group of LY3561774 and placebo for the mean percent change of ApoB from randomization at Visit 2 to Day 180 at Visit 9.

The primary analyses model will be MMRM as described in Section 9.3.1. Treatment comparisons will be performed at the full significance level of 0.05. Additional covariates may be added, and this analysis will be detailed in the SAP.

9.3.3. Secondary Endpoint(s) Analysis

Secondary endpoints are listed in Section 3.

The efficacy analyses for the secondary endpoints will use the EAS and MMRM analysis described in Section 9.3.1. The clinical measures for secondary endpoints may be log transformed before statistical analyses, if deemed necessary. This analysis will be detailed in SAP.

9.3.4. Tertiary/Exploratory Analysis

Exploratory endpoints are listed in Section 3.

The average of AUC (Day 120-180) and AUC (Day 210-270) of the ApoB reduction will be calculated for participants with complete ApoB measurements during the specified period.

The calculated AUCs will be analyzed using an ANCOVA model. Baseline ApoB measurements will be used for adjustment. A Bayesian approach will be used as the dose-response model for time averaged AUC measures. The placebo group will be modeled with LY3561774 doses.

Details of the prior distribution specifications along with other analyses used for the exploratory objectives will be provided in the SAP.

9.3.5. Safety Analyses

Safety assessments will be guided by an estimand comparing safety of LY3561774 doses with placebo irrespective of adherence to intervention. Thus, safety analyses will be conducted using the SS.

Adverse events will be coded from the actual term using the Medical Dictionary for Regulatory Activities (MedDRA) and reported with preferred terms and system organ class. Selected notable AEs of interest may be reported using high-level terms or Standardized MedDRA Queries.

Summary statistics will be provided for incidence of

- TEAEs
- SAEs
- study discontinuation due to AEs
- intervention discontinuation due to AEs
- deaths, and
- other cardiovascular endpoints.

Counts and proportions of participants experiencing AEs will be reported for each treatment group, and Fisher's exact test will be used to compare the treatment groups.

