2.3.3. Overall Benefit Risk Conclusion

Considering the measures taken to minimize risk for the participants in this study, the potential risks identified in association with LY3561774 are justified by the anticipated benefits that may be afforded to participants with mixed dyslipidemia.

3. Objectives, Endpoints, and Estimands

Objectives	Endpoints
Primary	
To evaluate if LY3561774 is superior to placebo for the treatment of mixed dyslipidemia in adults.	Percent change from baseline at Day 180 for ApoB.
Secondary	
Compare the clinical response of LY3561774 to placebo.	Percent change from baseline at Day 180 for 
 • ANGPTL3 • LDL-C • HDL-C • Non-HDL-C, and • Triglycerides.
	Percent change from baseline at Day 270 for 
 • ANGPTL3 • Non-HDL-C • LDL-C • HDL-C • ApoB, and • Triglycerides.
Characterize the pharmacokinetics (PK) of LY3561774.	Plasma concentrations of LY3561774.
Compare the effect of LY3561774 to placebo on safety endpoints.	Frequency of treatment-emergent adverse events.
To describe the safety of LY3561774 in participants with mixed dyslipidemia	Summary of safety data, including number and incidence of 
 • TEAEs • SAEs, and • discontinuations due to AEs.
Exploratory	
Assess the relationship between LY3561774 dose and clinical endpoints and potential participant factors that may influence these relationships.	Dose-response analyses for key efficacy and safety parameters.

Objectives	Endpoints
Assess the relationship between LY3561774 exposure and clinical endpoints and potential participant factors that may influence these relationships.	Exposure-response analyses for key efficacy and safety parameters.
Evaluation of immunogenicity.	Incidence of treatment-emergent anti-drug antibodies (ADA).
Compare the effect of LY3561774 to placebo on clinical endpoints or biomarkers.	Percent change from baseline at Day 180 for 
 • hsCRP • ApoA-I • ApoC-III • VLDL-C • UACR • HbA1c, and • FG.
Compare the effect of LY3561774 to placebo for key efficacy parameters.	Absolute change from baseline at Day 180 for 
 • Non-HDL-C • LDL-C • HDL-C • ApoB, and • Triglycerides.
Compare the effect of LY3561774 to placebo on hepatic fat fraction.	Change from baseline for MRI hepatic fat fraction at Day 180.

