For continuous measures, summary statistics will include sample size, mean, standard deviation (SD), median, minimum, and maximum for both the actual and the change from baseline measurements. Least squares (LS) means and standard errors derived from the analysis models, mixed model repeated measures (MMRM) and analysis of covariance (ANCOVA) will also be displayed for the change from baseline measurements. Treatment comparisons will be displayed showing LS means and 95% CIs for treatment differences, along with p-values for treatment comparisons. For categorical measures, summary statistics will include sample size, frequency, and percentages. A logistic regression model will be used to examine the treatment difference in binary efficacy outcomes with missing endpoints imputed. Fisher's exact test or Pearson's chi-square test will be used for treatment comparisons in other categorical outcomes.

For analyses of efficacy parameters involving an ANCOVA model, missing data will be imputed using the multiple imputation method under the missing at random assumption. Such an approach is valid when the propensity for a data point to be missing is not related to the missing data, but is related to some of the observed data. Estimates and standard errors from multiple imputed datasets will be combined using Rubin's rules.

Endpoints that compare treatment groups based on percent change from baseline will be conducted by log-transformation of the dependent variables. Standard errors and 95% CIs will be constructed using the delta method. The LS means and standard error for each treatment, difference in LS means between arms, and corresponding 95% CIs will be calculated as shown in Table EZCB.4.1, where Z_b is the baseline of the log of the response.

Table EZCB.4.1 Summary of Reported Quantities for Variables Requiring Log-Transformation

Qua	nntity	Change from Baseline	Percent Change from Baseline
Within	Estimate	$\left[\exp\left(\hat{\mu}_{\Delta Z,k} ight) - 1 ight]\exp(ar{Z}_{b\cdot})$	$\left[\exp\left(\hat{\mu}_{\Delta Z,k}\right)-1\right] imes 100$
Treatment	SE	$\exp(\overline{Z}_{b.})\exp(\hat{\mu}_{\Delta Z,k})\cdot\widehat{SE}_{\Delta Z,k}$	$\exp(\hat{\mu}_{\Delta Z,k}) \cdot \widehat{SE}_{\Delta Z,k} \times 100$
	P-value	NR	p_k
Between- Treatment Difference	Estimate	$[\exp(\hat{\mu}_{\Delta Z,k}) - \exp(\hat{\mu}_{\Delta Z,R})] \cdot \exp(\bar{Z}_b)$	$(\exp(\hat{\mu}_{\Delta Z,k\ vs\ R})-1)\times 100$

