4.6.2. Adverse Events

A TEAE is defined as an event that first occurred or worsened in severity after first dose. The Medical Dictionary for Regulatory Activities (MedDRA) Lowest Level Term (LLT) will be used in the treatment-emergent derivation. The maximum severity for each LLT during the baseline period, including ongoing medical history, will be used as baseline severity. Events with a missing baseline severity will be treated as "mild" in severity for determining treatment-emergence. Events with a missing severity during the postbaseline period will be treated as "severe" and treatment-emergence will be determined by comparing to baseline severity.

For events occurring on the day of first taking study medication, the case report form collected information (for example, treatment emergent flag, start time of study treatment, and event) will be used to determine whether the event was pre- versus post-treatment if available. If the relevant information is not available, then the events will be counted as posttreatment.

The counts and percentages of participants with TEAEs will be summarized by treatment using MedDRA Preferred Term (PT) nested within the System Organ Class (SOC). Statistical comparisons will be applied at both the SOC and PT levels. Events will be ordered by decreasing frequency within SOC. The SOC will be in alphabetical order. For events that are sex-specific, the denominator and computation of the percentage will include only participants from the given sex

An overview of the number and percentage of participants who experienced a TEAE, serious adverse event (AE), death, discontinued from study treatment or study due to an AE, and TEAE relationship to study drug will be summarized by treatment.

The counts and percentages of patients with TEAEs by maximum severity will be summarized by treatment using MedDRA PT. For each participant and TEAE, the maximum severity for the MedDRA PT is the maximum postbaseline severity observed from all associated LLTs mapping to the MedDRA PT. The maximum severity will be determined based on the non-missing severities. If all severities are missing for the defined postbaseline period of interest, it will show as missing in the table.

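### The placebo comparison of adverse-event frequency specifies a p-value but no risk difference or confidence interval

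*Protocol*

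**What the plan says.** Protocol Section 3 lists as a secondary objective "Compare the effect of LY3561774 to placebo on safety endpoints", with TEAE frequency as the endpoint. A separate secondary objective is to describe safety. SAP 1.1 repeats both.

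Protocol 9.3.5 sets out the analysis in one sentence. It opens with the per-arm output: "Counts and proportions of participants experiencing AEs will be reported for each treatment group". It then names the test: "Fisher's exact test will be used to compare the treatment groups". SAP 4.6.2 adds tables by system organ class and preferred term, tables by maximum severity, and an overview of TEAEs, serious events, deaths and discontinuations. On comparison it says only "Statistical comparisons will be applied at both the SOC and PT levels". SAP 4.1 names the tests: "Fisher's exact test or Pearson's chi-square test will be used for treatment comparisons in other categorical outcomes".

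Intervals appear in two places. For continuous measures, SAP 4.1 states "Treatment comparisons will be displayed showing LS means and 95% CIs for treatment differences, along with p-values for treatment comparisons". Protocol 9.3.1 gives a general rule. On testing it reads "all tests of treatment effects will be conducted at a 2-sided alpha level of 0.05"; on estimation it adds only that "confidence intervals will be calculated at 95%, 2-sided". SAP 4.1 repeats that rule. It fixes a level but attaches no interval to adverse-event incidence.

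**The concern.** An objective to compare needs a comparative result. For lipids and other continuous measures the plan gives an estimated difference with an interval. For adverse events it gives two or more percentages and a p-value. A p-value does not say how large an excess the data still allow, and in arms of 25 to 50 that excess can be sizeable when p is far above 0.05.

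This matters because the trial is meant to inform dose decisions (Protocol 2.1), and Protocol 2.3.1 names hepatobiliary events, hypersensitivity and injection-site reactions as potential risks. As written, nothing pre-specified puts an upper bound on the excess risk at each dose to set beside the ApoB effect.

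**Working it through.** **Inputs from the documents**
- About 175 randomised at 2:1:2:2 (Protocol 9.5). The ratio sums to 7 and 175/7 = 25, so placebo 50, 100 mg 25, 400 mg 50, 800 mg 50.
- The safety set is everyone randomised and dosed, whatever their adherence (Protocol 9.2). The SAP also removes participants discontinued for inadvertent enrolment. The denominators are therefore about 50/25/50/50, not the completer numbers of 40/20/40/40.
- Two-sided alpha of 0.05, with no multiplicity adjustment (Protocol 9.3.1, SAP 2.1).

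**Assumptions.** The documents give no adverse-event rate, no clinically relevant excess and no safety power. All event rates and counts below are illustrative.

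**The plan's own power figure.** This exists only for ApoB: difference 30, SD 15, completers. For 40 v 40, SE = 15 × √(1/40 + 1/40) = 3.35 and 30/3.35 = 8.9. For 20 v 40, SE = 15 × √(1/20 + 1/40) = 4.11 and 30/4.11 = 7.3. Both give power above 99.99%, so the stated >99% reproduces. It says nothing about safety.

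**Power of Fisher's test.** Power is the sum, over all pairs of event counts (x placebo, y active) with two-sided Fisher p ≤ 0.05 and a higher rate on active, of Bin(x; 50, p₀) × Bin(y; n, p₁), with n = 50 or 25.

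| Placebo v active | 50 v 50 | 50 v 25 (100 mg) |
|---|---|---|
| 0% v 10% | 38% | 46% |
| 5% v 15% | 24% | 27% |
| 10% v 20% | 20% | 18% |
| 50% v 60% | 13% | 11% |
| 10% v 30% | 64% | 51% |
| 5% v 30% | 90% | 79% |
| 0% v 20% | 95% | 90% |

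For a 10-point excess, power runs from 11% to 46%, so the test misses it in 54% to 89% of trials. Excesses of 20 to 25 points fare better, but this depends on the placebo rate: 50% v 70% has only 46% and 35% power.

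**What an interval would add.** Newcombe's method combines the Wilson limits (l, u) of each arm. With d = p₁ − p₀:
- upper limit = d + √[(u₁ − p₁)² + (p₀ − l₀)²]
- lower limit = d − √[(p₁ − l₁)² + (u₀ − p₀)²]

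For 5/50 the Wilson limits are 4.35% and 21.36%. With 5/50 in both arms, d = 0 and the upper limit is √(11.36² + 5.65²) = 12.7 points.

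| Active v placebo | Fisher p | Difference, points (95% CI) |
|---|---|---|
| 5/50 v 5/50 | 1.00 | 0 (−12.7 to +12.7) |
| 10/50 v 5/50 | 0.26 | +10 (−4.3 to +24.2) |
| 5/25 v 5/50 | 0.29 | +10 (−5.9 to +29.9) |
| 30/50 v 25/50 | 0.42 | +10 (−9.2 to +28.2) |

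Each row is non-significant, yet each leaves room for an excess of more than 12 points.

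**The case against.** Per-arm counts and percentages are planned, at several levels of detail, so a reader can subtract them and compute an interval. That stands, and it rules out the reading that the objective is answered by p-values alone. What is missing is a pre-specified between-arm estimate with its uncertainty.

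A reader might also infer that Fisher's test misses most clinically relevant harms at these sizes. The documents do not support this. They define neither a relevant excess nor a background rate, and some larger excesses are usually detected, as the 5% v 30% and 0% v 20% rows show. Low power comes from arm size, which was set on ApoB. That is ordinary in Phase 2, and adding an interval changes no miss rate.

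Nor do the documents plan any claim that a dose does not differ from placebo on safety. Much of the safety review does not depend on p-values: narratives, liver-threshold tables and screening plots, participant profiles, adjudicated cardiovascular events and triggered unblinded review. The hepatic-disorder, hypersensitivity and injection-site summaries in SAP 4.6.7 name no Fisher test of their own. These points limit the concern to the missing estimate. They do not supply it.

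**Conclusion.** The point holds in this limited form. For a stated comparative objective, the only between-arm result specified is a Fisher or Pearson p-value, and no risk difference or interval is named for adverse events. Under assumed placebo rates of 0% to 50%, power for a 10-point excess is about 11% to 46%, so p > 0.05 is weak evidence against an excess of that size. The power figures rest on those assumed rates and on about 50/25/50/50 in the safety set; the gap in the specification rests on neither. No primary result, error rate or estimand is affected. It is a cheap improvement in how safety results are reported, not a flaw in sample size.

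**What to change.** In SAP 4.6.2, for the overview rows (any TEAE, serious adverse event, discontinuation due to an adverse event), report for each dose the risk difference from placebo with a two-sided 95% confidence interval, by Miettinen-Nurminen or Newcombe, and name which. Do the same for the combined hepatic, hypersensitivity and injection-site categories in SAP 4.6.7. State that adverse-event p-values are descriptive flags and that p > 0.05 is not to be read as absence of excess risk. Intervals for every sparse preferred term are not needed.

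The cost is SAP wording and a few more table columns: three differences and three intervals per row, from data already tabulated. The intervals will be wide, so safety statements will become more cautious. They do not invert Fisher's test and can disagree with it near the boundary: 5/50 v 0/50 gives p = 0.056, but a Newcombe interval of +0.9 to +21.4 points. The SAP should therefore say that the estimate and interval lead. No change to design, dosing or data collection is involved.
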